Study protocol

México CDMX. a January 20th 2016

Effect of Acute or Chronic Ingestion of Sucralose on Serum Insulin in Young and Healthy Adults: A Randomized, Double-Blind, Placebo-Controlled Trial.

Background

Relevance of the estudy

Hypothesis

Principal outcome

Materials and Methods

Ethical considerations

México CDMX. a January 20th 2016

Effect of Acute or Chronic Ingestion of Sucralose on Serum Insulin in Young and Healthy Adults: A Randomized, Double-Blind, Placebo-Controlled Trial.

Background

Since the last 30 years, the prevalence of overweight and obesity have been considerably increasing worldwide (1); this is directly associated with a greater incidence of non-transmissible chronic disease such as Type 2 Diabetes Mellitus (DM2) (2, 3). Consequently, in recent years the consumption of Non-Caloric Sweeteners (NCS) has increased in young and healthy adults as a healthy alternative to reduce the ingestion of calories with the sweet taste in food or beverages (4). One of the NCS (No Caloric Sweetener) more consumed in the world is the sucralose, because is the 600 times sweeter than sugar but without calories intake (5, 6).

Nevertheless, there are some studies that suggest a correlation between high consumption of NCS and high levels of blood glucose, insulin, and metabolic hormones as C-peptide, Gastric Inhibitory Polypeptide (GIP) and Glucagon-Like Peptide-1 (GLP-1), these systemic inflammatory factors can have an impact role on the development of DM2, obesity and cardiovascular diseases (7). On the other

hand, a study in animal models shown that the chronic exposure to sucralose for 10 weeks increases the values of area under the curve (AUC) of glucose tolerance test, which was attributed to a change of the intestinal microbiota (8). However, these studies did not take in to consideration the effect of acute or chronic exposure to NCS over the systemic inflammatory response; which has been repeatedly documented as a previous step in the development of glucose intolerance in the obese patient (9-11).

Furthermore, it has not been studied until now whether the acute or prolonged consume of NCS such as sucralose is capable to cause a systemic inflammatory state and if this is related to the development of glucose intolerance in healthy individuals. This has generated in the scientific community a polemical discussion about the possible association between the consume of sweeteners and the development of glucose intolerance; which is characterized by the elevation in the AUC of insulin, glucose, C peptide, glucagon, GIP and GLP-1, as well as the rise of systemic inflammatory factors. Whence the aim of this research was measure the effect of the acute and chronic exposure to sucralose on blood glucose, insulin, C-peptide, GIP and GLP-1 levels and the reduction of interleukins 4, 10, 13 in young and healthy adults.

Relevance of the study

Until now, the international agencies safety assessment of non-caloric sweeteners has been enough to recommend their use in humans. This confidence has led to a mass production and use of these additives for the western population of all ages, complemented by the absence of epidemiological evidence focused on trade

adversities to the consumption of these substances. However, recent studies have revealed some studies that relate a state of glucose intolerance and insulin resistance with the chronic consumption of some of these available in the market products, as in the case of sucralose. Unfortunately, the results of these studies have been criticized for the lack of methodology robustness used and for omitting the presence of other markers that are directly involved with metabolic dysfunctions; the only consideration was the symptom of sucralose on the intestinal microbiota. Therefore, it is necessary to determine if the acute or chronic consumption of sucralose is capable of inducing a glucose intolerance and insulin resistance state in humans, through the performance of a dependable robust prospective, randomized, double blind study and placebo controlled, which allows us to issue reliable recommendations on the habitual use of non-caloric sweeteners in our population.

Hypothesis

In healthy, young volunteers, subjected to an oral glucose tolerance curve of 180 minutes, acute or chronic exposure to 48 - 96 mg of sucralose in a single dose or 10 weeks daily intake, respectively, causes an increase in the average levels of the area under the curve of insulin, glucose and other intolerance to this carbohydrate markers when compared with water as a placebo.

Principal outcome

To evaluate the effect of acute and chronic exposure to 48 - 96 mg of sucralose in a single dose or for 10 weeks, respectively, on the average levels of the area under

the insulin curve in healthy, young volunteers, subjected to an oral glucose tolerance curve at 180 minutes, in a randomized, double-blind, placebo-controlled study.

Materials and Methods

This is a randomized, double-blind, placebo-controlled trial in young and healthy adults, the study at the General Hospital of Mexico, [name] from April 2016 to June 2018, and the present study meets with the criteria of CONSORT.

To evaluate the acute effect of sucralose, the experimental groups will receive 48 mg / 60 ml and 96 mg / 60 ml of fasting sucralose in a single shot, while the control group will receive 60 ml of water as a placebo, before undergoing a CTOG with 75 g of glucose during 180 min. During this procedure, 4 ml of blood will be taken at -15 (sucralose intake or placebo) and 0 (75 g glucose intake) as a base and then at 15, 30, 45, 60, 75, 90, 105, 120 and 180 minutes post-load glucose for the quantification of insulin, glucose, C-peptide, glucagon, GLP-1, and GPI levels. Subsequently, to evaluate the chronic effect of sucralose, the experimental group will continue with the daily intake of 48 – 96 mg / 60ml of sucralose for 10 consecutive weeks, while the control group will receive 30 ml of water daily as a placebo during the same period of time. At the end of 10 weeks of treatment with sucralose or placebo, a second CTOG (75g / 180 min) will be carried out, taking again 4 ml of blood at -15 and time zero, and subsequently 4 ml at 15, 30, 45, 60, 75, 90, 105, 120 and 180 minutes after glucose loading. To evaluate the acute exposure to the sweetener, the area under the curve (AUC) of the blood glucose levels obtained during the CTOG in each participant will be calculated and the average differences

between the sucralose groups versus placebo will be compared, adjusting for BMI. In the case of chronic exposure to the sweetener, the AUC values between the sucralose groups versus placebo will be compared after 10 weeks, and the AUC values will be compared at the beginning and end of the study in the group that received sucralose, adjusting in both cases for BMI. In addition to the determination of glucose levels during the two CTOGs, the circulating levels of insulin, glucagon, C peptide, GIP, GLP-1, TNF- α , pCr, IFN- γ , IL-1 β , IL-4, IL-6, IL-10, IL-12, IL-13, IL-17, IL-23, and inflammatory monocytes CD14hiCD16 + CD11c + CCR2hiCX3CR1lowCD206-, with the purpose of comparing their values in the acute exposure scheme and chronic to sucralose, adjusting for BMI. The samples of excrement from acute and chronic exposure will be processed to extract the DNA and run them in PCR in real time and the percentage of each bacteria present in feces will be compared at the beginning and at the end. The difference between the two samples will be analyzed by means of square chi.

Ethical considerations

This study will be carried out in compliance with the guidelines of the protocol, with the ethical principles of the Declaration of Helsinki in its most recent version approved during the 64th Assembly of the World Association of Physicians, in Fortaleza Brazil, in October 2013, in accordance to the principles that govern human research in the General Health Law and in accordance with the ethical and research guidelines of the General Hospital of Mexico "[name].

REFERENCES

3. Garcia LM, da Silva KS, Del Duca GF, da Costa FF, Nahas MV. Sedentary behaviors, leisure-time physical inactivity, and chronic diseases in Brazilian workers: a cross sectional study. *J Phys Act Health.* 2014;11(8):1622-34.

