Statistical Analysis Plan

México CDMX. January 20th 2016

Effect of Acute or Chronic Ingestion of Sucralose on Serum Insulin in Young and Healthy Adults: A Randomized, Double-Blind, Placebo-Controlled Trial.

The statistical analysis will help us to provide accurate and quantifiable data in order to increase the documented information about the sucralose; this analysis will also help us to have a better reliability on the study results.

Estimation of sample size

Considering the results on the difference of the averages of the areas under the curve for plasma insulin in obese volunteers exposed to sucralose and water, before an oral glucose load, as reported by Pepino et al., [1], the estimation of the Sample size was:

t tests - Means: Difference between two independent means (two groups)

Analysis: A priori: Compute required sample size

Input:

Tail(s)	=	One
Effect size d	=	0.419231264
α err prob	=	0.05
Power (1- β err prob)	=	0.8
Allocation ratio N2/N1	=	1

Output:

Noncentrality parameter δ	=	2.5153876
Critical t	=	1.6556552
Df	=	142
Sample size group 1	=	72
Sample size group 2	=	72
Total sample size	=	144
Actual power	=	0.8046976

For the estimation of the sample size the program GPower version 3.1.9.2 (University of Düsseldorf, Germany) was used. The difference between two

averages was estimated by means of a test of t, of an address, with an alpha value (0.05), assuming unequal variances, for a power of proof of 80%, a value of Cohen of 0.419231264, the sample size is 72 volunteers per group, the total sample size is left in 144 volunteers.

The demographic analysis will be assessed with descriptive statistics, ensuring the two groups are balanced in their moments for the main variables.

The statistical analysis of the presence or occurrence of any inflammatory process during the the study will be carried out by comparing the before / after differences between the sucralose and water groups for the whole sample, adjusting for BMI, these differences will be compared for each analyte related to chronic inflammation such as C-reactive protein, tumor necrosis factor-alpha, interleukin (IL) 6, IL-12, IL-10 and inflammatory monocytes CD11c + CCR2High.

In order to calculate the area under the glucose tolerance test curve will be assessed using the trapezium method [2] for glucose, insulin, C-peptide, glucagon GPI and GLP-1.

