The statistical analysis of the oral glucose tolerance curves will be carried out by means of an analysis of variance test for repeated measurements and for the area under the curve of each of the metabolic analytes.

For each of the differences between the area under the initial and final curve of glucose, insulin, C-peptide, glucagon, GPI and GLP-1 between sucralose and water, an ANCOVA will be made, taking the BMI as a covariate.

For the analysis of the behavior of the intestinal microbiota, a comparison of the percentages of the flora between the first and the last sample of excrement will be carried out, and a chi square test will be applied.

The correlation between the initial HOMA-IR value and the glucosylated hemoglobin will be explored.

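### Beside the placebo comparison, the protocol tests chronic exposure by start-versus-end AUC within sucralose alone, and neither document says which comparison decides

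*Protocol*

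**What the plan says.** The chronic-exposure sentence in Materials and Methods of the protocol contains two analyses:

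- A randomised one: "the AUC values between the sucralose groups versus placebo will be compared after 10 weeks".
- A within-group one: "the AUC values will be compared at the beginning and end of the study in the group that received sucralose".

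It closes with "adjusting in both cases for BMI", so both are planned analyses. Neither is labelled primary, supportive or descriptive, and no start-versus-end comparison is mentioned for the water arm. That arm is nevertheless followed alongside: "the control group will receive 30 ml of water daily as a placebo during the same period of time". It also has the second glucose tolerance curve.

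The SAP approaches change over time differently. For the "differences between the area under the initial and final curve of glucose, insulin, C-peptide, glucagon, GPI and GLP-1 between sucralose and water", it says that "an ANCOVA will be made, taking the BMI as a covariate". Inflammatory markers are handled in the same way, by "comparing the before / after differences between the sucralose and water groups". The SAP neither repeats the sucralose-only test nor withdraws it, and it gives no order of importance among the analyses.

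**The concern.** The protocol's hypothesis is framed against water, and the within-sucralose test does not address it. A second glucose tolerance test 10 weeks after the first can differ because of familiarity with the procedure, season, diet, assay batch or weight change. The water arm experiences the same influences, so a between-arm comparison cancels them. A start-versus-end test in one arm counts them as part of the sucralose effect.

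The stated BMI adjustment does not solve this. If BMI is taken once at entry, it is constant within a person and cannot account for a shift common to everyone. If it is taken at both visits, the second value comes after randomisation. The documents do not say which is meant.

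At stake is the chronic half of the principal outcome. With two unranked tests, a placebo-controlled trial could report a chronic effect on an uncontrolled before/after result while the randomised contrast shows nothing.

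**Working it through.** **1. The plan's own figure.** Inputs from the SAP, Estimation of sample size: two independent means, one-sided alpha 0.05, d = 0.419231264, allocation 1:1, 72 per group. Noncentrality = d × √(n/2) = 0.419231264 × √36 = 2.5154; df = 142; critical t = 1.6557; power = 0.8047. With 71 per group the power is 0.7998. The stated 72 per group is reproduced. It is a calculation for a comparison between arms, not for a before/after test.

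**2. Behaviour of the within-sucralose test when sucralose does nothing.** The documents give neither a drift nor a visit-to-visit correlation, so both are assumed. Let drift be the mean start-to-end shift shared by both arms, in SD units of AUC, and let r be the correlation between visits. The test is taken as a paired t test, without the BMI term:

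- standardised change: dz = drift / √(2(1 − r))
- noncentrality: dz × √n, with df = n − 1

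With n = 72 and r = 0.6, √(2 × 0.4) = 0.894:

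| Drift (SD) | dz | Noncentrality | Significant, one-sided 0.05 | Significant, two-sided 0.05 |
|---|---|---|---|---|
| +0.1 | 0.112 | 0.949 | 24.0% | 15.5% |
| +0.2 | 0.224 | 1.897 | 59.3% | 46.5% |
| −0.1 | −0.112 | −0.949 | 0.5% | 15.5% |
| −0.2 | −0.224 | −1.897 | 0.02% | 46.5% |

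**3. Sensitivity at +0.2 SD, one-sided.**

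- Correlation, with n = 72: 45.6% at r = 0.4, 51.4% at 0.5, 70.0% at 0.7.
- Number analysed, with r = 0.6: 37% at n = 36, 85% at n = 144. The range is needed because the protocol describes two sucralose dose groups while the SAP sizes two groups in all, so the number behind the sucralose group is not fixed.

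**4. The randomised contrast.** A drift shared by both arms drops out of the difference between arms, so that test stays at 5% under every drift above.

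**5. Effect of having no ranking.** If either the 10-week between-arm test or the within-sucralose test could support a claim (simulation, n = 72 per arm, r = 0.6, one-sided), the chance of at least one false positive is about 9% with no drift, 27% at +0.1 SD and 60% at +0.2 SD.

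**The case against.** The controlled analyses are already in the plan. The 10-week placebo comparison stands in the same sentence as the within-group test. The SAP names insulin among the analytes whose start-to-end change is compared between sucralose and water. The hypothesis and the sample size are also between-arm. A reader who sees only the within-group clause might infer that the 10-week effect is tested inside the sucralose group alone, so that any time trend would automatically count as a chronic effect. The documents do not support that reading.

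Three further points are fair:

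- The protocol introduces AUC in this paragraph as glucose AUC and brings in insulin afterwards. Applying the within-group test to insulin AUC is therefore an inference, though a natural one given the principal outcome.
- A reader might take the protocol's Background as linking sweetener use directly to obesity, so that adjusting for BMI would remove an effect acting through weight. The statement that certain factors "can have an impact role on the development of DM2, obesity and cardiovascular diseases" has systemic inflammatory factors as its subject. It does not carry that argument, and the timing of the BMI measurement is simply left open.
- Drift may go either way. Downward drift makes a one-sided false positive rarer, not commoner.

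What remains is that the sound analyses protect the conclusion only if they decide it, and nothing in either document says that they do.

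**Conclusion.** The point holds in a limited form. The protocol lists an uncontrolled start-versus-end test in the sucralose group beside a sound randomised comparison, as an unranked second test of chronic exposure. The harm is conditional: it arises if that test is used as evidence of a chronic effect and AUC drifts for reasons unrelated to sucralose. Under the illustrative assumptions (n = 72, correlation 0.6, shared drift of +0.1 to +0.2 SD) the one-sided false-positive rate is about five to twelve times the nominal 5%. A downward drift biases the same test against a real increase. None of these inputs comes from the documents, so the figures show how sensitive the test is and do not predict what this trial will find. The randomised contrasts already planned are not affected by shared drift.

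**What to change.** In the chronic-exposure sentence of the protocol's Materials and Methods, state that conclusions about chronic exposure rest only on the randomised sucralose-versus-water contrast, in line with the SAP's between-arm ANCOVA of change in AUC. Replace the within-sucralose test by a descriptive table of start-to-end change with confidence intervals for every arm, including water, and say that no within-arm test will be used as evidence of a chronic effect. Put the same statement in the SAP.

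While making the edit, say when the BMI covariate is measured.

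The change is to wording only. The water arm's second curve is already being collected. The sponsor gives up one uncontrolled p-value.

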Statistical Analysis Plan

México CDMX. January 20th 2016

Effect of Acute or Chronic Ingestion of Sucralose on Serum Insulin in Young and Healthy Adults: A Randomized, Double-Blind, Placebo-Controlled Trial.

The statistical analysis will help us to provide accurate and quantifiable data in order to increase the documented information about the sucralose; this analysis will also help us to have a better reliability on the study results.

Estimation of sample size

Considering the results on the difference of the averages of the areas under the curve for plasma insulin in obese volunteers exposed to sucralose and water, before an oral glucose load, as reported by Pepino et al., [1], the estimation of the Sample size was:

t tests - Means: Difference between two independent means (two groups)

Analysis: A priori: Compute required sample size

Input:

Tail(s)	=	One
Effect size d	=	0.419231264
α err prob	=	0.05
Power (1- β err prob)	=	0.8
Allocation ratio N2/N1	=	1

Output:

Noncentrality parameter δ	=	2.5153876
Critical t	=	1.6556552
Df	=	142
Sample size group 1	=	72
Sample size group 2	=	72
Total sample size	=	144
Actual power	=	0.8046976

For the estimation of the sample size the program GPower version 3.1.9.2 (University of Düsseldorf, Germany) was used. The difference between two

averages was estimated by means of a test of t, of an address, with an alpha value (0.05), assuming unequal variances, for a power of proof of 80%, a value of Cohen of 0.419231264, the sample size is 72 volunteers per group, the total sample size is left in 144 volunteers.

The demographic analysis will be assessed with descriptive statistics, ensuring the two groups are balanced in their moments for the main variables.

The statistical analysis of the presence or occurrence of any inflammatory process during the the study will be carried out by comparing the before / after differences between the sucralose and water groups for the whole sample, adjusting for BMI, these differences will be compared for each analyte related to chronic inflammation such as C-reactive protein, tumor necrosis factor-alpha, interleukin (IL) 6, IL-12, IL-10 and inflammatory monocytes CD11c + CCR2High.

In order to calculate the area under the glucose tolerance test curve will be assessed using the trapezium method [2] for glucose, insulin, C-peptide, glucagon GPI and GLP-1.

The statistical analysis of the oral glucose tolerance curves will be carried out by means of an analysis of variance test for repeated measurements and for the area under the curve of each of the metabolic analytes.

For each of the differences between the area under the initial and final curve of glucose, insulin, C-peptide, glucagon, GPI and GLP-1 between sucralose and water, an ANCOVA will be made, taking the BMI as a covariate.

For the analysis of the behavior of the intestinal microbiota, a comparison of the percentages of the flora between the first and the last sample of excrement will be carried out, and a chi square test will be applied.

The correlation between the initial HOMA-IR value and the glucosylated hemoglobin will be explored.

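### The SAP's 80% power is for a one-sided, unadjusted t-test, but the planned ANOVA and ANCOVA carry no tail or alpha, so sizing and analysis need to be aligned

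*SAP*

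**What the plan says.** **Sizing.** Under Estimation of sample size, the SAP shows output for two independent means: one tail, alpha 0.05, d = 0.419231264, 72 per group, 142 degrees of freedom, power 0.8046976. The prose repeats the choice of test: "a test of t, of an address, with an alpha value (0.05), assuming unequal variances, for a power of proof of 80" per cent.

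**Analysis.** The SAP's later paragraphs analyse the glucose tolerance curves by "an analysis of variance test for repeated measurements and for the area under the curve of each of the metabolic analytes". For the difference between initial and final AUC "between sucralose and water, an ANCOVA will be made, taking the BMI as a covariate". Neither sentence gives a significance level, a tail or a directional contrast.

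**Protocol.** The Hypothesis is directional: sucralose "causes an increase in the average levels of the area under the curve of insulin". The Principal outcome is worded neutrally: "To evaluate the effect of acute and chronic exposure to 48 - 96 mg of sucralose". Materials and Methods says that AUC values "between the sucralose groups versus placebo will be compared, adjusting for BMI", without naming a test. It also describes two dose levels: "the experimental groups will receive 48 mg / 60 ml and 96 mg / 60 ml of fasting sucralose in a single shot".

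**The concern.** The only tail and alpha in either document belong to the sample-size estimate, and the t-test sized there does not appear in the analysis text. An analyst who follows the analysis paragraphs in the usual way would report a non-directional F-test, or a two-sided p-value for the treatment term. That is not the test with the stated 80%.

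The choice can decide the trial's main result. With 142 degrees of freedom, a t statistic between 1.656 and 1.977 in the direction of an increase is significant under the sizing rule and not significant under the usual F-test. Two careful analysts could reach opposite conclusions on insulin AUC, and settling that choice before the data are seen is a main purpose of a SAP.

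**Working it through.** **Inputs.** From the SAP's Estimation of sample size: d = 0.419231264, n = 72 per group, alpha = 0.05, one tail. The documents do not give the correlation r between the two visits' AUCs or the share R² of AUC variance explained by BMI. The values used for them below are assumptions.

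**1. Reproduce the plan's figure.** Noncentrality δ = d·√(n/2) = 0.419231264 × √36 = 0.419231264 × 6 = 2.5154. Degrees of freedom = 72 + 72 − 2 = 142. The one-sided critical t is 1.6557. Power = P(noncentral t > 1.6557) = 0.8047, which matches the SAP's 0.8046976.

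**2. Same inputs, two-sided.** δ is unchanged and the critical t becomes 1.9768. Power = 0.7048. The F-test on 1 and 142 degrees of freedom with λ = δ² gives the same 0.7048. Spending one degree of freedom on BMI, with no reduction in variance, leaves both figures unchanged to four decimals (0.8047 and 0.7048).

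**3. What two-sided 80% would need.** With 72 per group, d = 0.47. With d = 0.419, 91 per group (182 in total): 90 gives 0.7987 and 91 gives 0.8031.

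**4. The planned analysis is of AUC change.** If d is in single-visit SD units and the SDs are equal at both visits, the standardised difference in change is d/√(2(1 − r)). A BMI adjustment divides d by √(1 − R²).

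| Assumption | Effective d | Two-sided | One-sided |
|---|---|---|---|
| r = 0.3, no BMI gain | 0.354 | 56.0% | 68.1% |
| r = 0.5, no BMI gain | 0.419 | 70.5% | 80.5% |
| r = 0.7, no BMI gain | 0.541 | 89.7% | 94.4% |
| single AUC, R² = 0.10 | 0.442 | 75.0% | 84.0% |
| single AUC, R² = 0.20 | 0.469 | 79.8% | 87.6% |
| r = 0.7 and R² = 0.20 | 0.605 | 95.0% | 97.5% |

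Two-sided power reaches 80% at about r = 0.60 without BMI gain, or at about R² = 0.205 for a single AUC. At r = 0.3 without BMI gain, even the one-sided test falls short of 80%.

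**The case against.** The strongest reply is that the documents are silent here and do not contradict themselves. The SAP states one tail twice and gives alpha 0.05, and the protocol's hypothesis predicts an increase. In so short a plan, the one-sided rule could be meant to govern the insulin comparison throughout. A two-group ANCOVA has a treatment contrast on one degree of freedom with a signed t statistic, so it can be tested one-sided. The neutral Principal outcome is ordinary wording for an objective and is weak evidence the other way.

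Much of this stands. The one-sided reading is possible, and the sizing contains no arithmetic error. What remains is that a directional hypothesis is not a decision rule, and the default output of the named methods is non-directional. One sentence would settle it.

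A reader might infer that the trial's power is 70.5%, or that it is underpowered. The documents do not support either. The 70.5% belongs to a two-sided, unadjusted comparison of one AUC, whereas the planned ANCOVA is of change with BMI as a covariate. Its two-sided power ranges from 56% to 95% over the assumptions shown.

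It can also be said that the two-group frame matters as much as the tail, since the protocol describes two dose levels and water. That is fair. If the 144 were split equally into three groups (an assumption; no split is given), both doses pooled against water (96 versus 48) would have 76% power one-sided and 65% two-sided. One dose against water (48 versus 48) would have 65% and 53%. The overall three-group F-test would have two degrees of freedom, so its equivalence to the t-test would no longer hold.

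**Conclusion.** The point holds as an inconsistency between sizing and analysis. The stated 80% belongs to a one-sided test that the analysis text does not carry forward. On the SAP's own two-group basis the tail is worth about 10 percentage points: 80.5% against 70.5%. That comparison assumes 72 per group, d = 0.419 in SD units of the AUC measure analysed, and no gain from BMI.

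No shortfall below 80% is shown for the planned ANCOVA of change, and none can be ruled out, because r and R² are not given. It should be corrected because it concerns the only endpoint that was sized and the repair is small.

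**What to change.** First, name the principal insulin-AUC contrast: which AUC is tested (acute, week 10 or change), and that pooled sucralose is compared with water. Then make the test and the sizing agree by one of two routes.

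- **(a) Two-sided.** *The contrast is tested two-sided at 0.05 by ANCOVA with BMI. With 72 versus 72, power is about 70% for d = 0.419, or 80% for d = 0.47, where d is the standardised difference in the AUC measure analysed, before any gain from BMI adjustment.*
- **(b) One-sided.** *The 1-df ANCOVA contrast with BMI is tested one-sided at 0.05 in the direction of an increase. The 80% power applies only if d = 0.419 is in SD units of the AUC measure analysed.*

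Under either route, add: *The power figure assumes two groups of 72 and does not cover separate comparisons of 48 mg and 96 mg with water.*

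**Cost.** SAP wording only; no extra participants are proposed. Route (a) fits the usual ANOVA and ANCOVA tests but states a less favourable power; restoring 80% on the same inputs would take 91 per group instead of 72. Route (b) is the smaller edit and follows the sizing, but it cannot declare a lower insulin AUC under sucralose significant.

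### The SAP sizes two groups (72 + 72), but the protocol describes three; at 144 the stated 80% holds only for pooled sucralose v water at near-equal totals, and each dose tested separately has about 65%

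*SAP*

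**What the plan says.** **SAP, Estimation of sample size.** The calculation is for two independent groups at an allocation ratio of 1, one-sided alpha 0.05, Cohen's d = 0.419231264 and 80% power. It concludes that "the sample size is 72 volunteers per group, the total sample size is left in 144 volunteers". The rest of the SAP also speaks of two groups: the demographic paragraph has "ensuring the two groups are balanced in their moments for the main variables", and the AUC differences are to be analysed "between sucralose and water, an ANCOVA will be made, taking the BMI as a covariate".

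**Protocol, Materials and Methods.** In the acute phase, "the experimental groups will receive 48 mg / 60 ml and 96 mg / 60 ml of fasting sucralose in a single shot", with a separate control group on water. The analysis text says that average differences "between the sucralose groups versus placebo will be compared, adjusting for BMI". Both statements use the plural. The same section also uses the singular: "to evaluate the chronic effect of sucralose, the experimental group will continue with the daily intake of" a dose range of 48 to 96 mg, and later "the AUC values will be compared at the beginning and end of the study in the group that received sucralose".

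**Not stated in either document.** There is no number per arm for three arms, no statement that the doses are pooled or tested separately, and no named between-group contrast for insulin AUC. The SAP's ratio of 1 belongs to its two-group calculation.

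**The concern.** The 80% power is the only justification given for 144 participants. It was computed for two groups of 72, whereas the protocol's acute phase has three groups. A total of 144 also rules out reading 72 as the size of each of three arms, which would be 3 × 72 = 216.

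The wording allows at least two analyses: both doses pooled against water, or each dose against water. They have different power at the same total, and pooled power also depends on how many participants receive water. If this stays open, the doses could be pooled or split after the data are seen. A null result for one dose could also be read as coming from an 80%-powered test when its power was well below that.

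**Working it through.** **Inputs (SAP, Estimation of sample size):** d = 0.419231264; one-sided alpha 0.05; total 144. The three arms come from the protocol, Materials and Methods.

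**Formula.** For groups of n1 and n2, the noncentrality is δ = d × √(n1·n2/(n1+n2)) with df = n1 + n2 − 2. Power is the probability that a noncentral t(df, δ) exceeds the one-sided critical value.

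**Step 1: reproduce the SAP.** With 72 v 72, δ = 0.419231264 × √36 = 2.5154, df = 142, critical t = 1.6557 and power = 0.8047. All four match the SAP.

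**Step 2: pooled sucralose v water, 144 in total (df 142, critical t 1.6557).**

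| Sucralose v water | δ | Power |
|---|---|---|
| 72 v 72 | 2.5154 | 80.5% |
| 80 v 64 | 2.4998 | 80.0% |
| 96 v 48 (three equal arms) | 2.3715 | 76.3% |

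Power reaches 80% only with 64 to 80 participants on water.

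**Step 3: each dose v water, 144 in total, assuming each dose has the SAP's d.**

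| Dose v water | Arms (48 mg / 96 mg / water) | δ | One-sided 0.05 | Bonferroni, one-sided 0.025 |
|---|---|---|---|---|
| 48 v 48 | 48/48/48 | 2.0538 | 65.3% | 52.9% |
| 36 v 72 | 36/36/72 | 2.0538 | 65.4% | 53.0% |
| 42 v 60 | 42/42/60 | 2.0838 | 66.5% | 54.1% |

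The last row is the maximum over all splits with equal dose groups, so no such allocation of 144 brings a single-dose comparison near 80%.

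**Step 4: sensitivity to the effect size.** The documents do not say which dose d represents. If a single dose had 0.75 to 1.25 times d (an assumed range), its unadjusted power at 48 v 48 would run from 45% to 82%. Reaching 80% at 48 v 48 needs d = 0.511, and 0.511/0.419 = 1.22 times the SAP's value.

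**The case against.** The strongest reply is that the SAP is consistent within itself. It sizes, balances and analyses sucralose against water, and the protocol's Hypothesis and Principal outcome treat 48 to 96 mg as one exposure. On that reading, with the SAP's 1:1 ratio, the stated power is correct. No test of a single dose against water is written down, so the 65% belongs to an analysis that may not be intended, and the Bonferroni figures go a step further. The 65% also assumes the same d for both doses.

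Much of this stands. Pooling is the better-supported reading of the SAP, and the single-dose figures are conditional. But pooling is never stated, and the protocol's plural groups allow separate comparisons. Even under pooling, the 80% needs 64 to 80 on water, which neither document specifies for three arms.

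A second reply is that the planned ANCOVA on BMI will recover some power. How much cannot be computed from the documents. If BMI explained 5% or 10% of the AUC variance (assumed values), dividing d by √0.95 or √0.90 and using one fewer df would give 78.1% or 80.0% at 96 v 48. The single-dose comparison at 48 v 48 would still be only 69.3% at 10%. The SAP's own 80% takes no credit for this adjustment.

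**Conclusion.** The concern holds. The two documents disagree on the number of arms, and the stated 80% belongs to a two-group design. At 144 it is right for pooled sucralose v water with 64 to 80 on water. It is about 4 points too high for pooling across three equal arms (80.5% against 76.3%). It is about 15 points too high for each dose v water (80.5% against 65.3%), or about 28 points with Bonferroni (80.5% against 52.9%).

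These figures use the SAP's d and one-sided alpha, with no dropout and no gain from BMI adjustment. The single-dose figures also assume the same d for both doses. The disagreement on the number of arms and the missing contrast do not depend on any of these assumptions.

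**What to change.** Reconcile the protocol and the SAP on the number of arms, including the protocol's mix of singular and plural groups. State the number per arm and name the between-group contrast to which the power refers. Because the principal outcome covers both acute and chronic exposure, the statement should also say which phase it concerns. Then, keeping 144, do one of the following:

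- **(a) Pooled contrast powered.** Name pooled sucralose v water as the powered contrast and give its power at the actual allocation (80.5% at 72 v 72, 76.3% at 96 v 48). Label single-dose comparisons as secondary, with about 65% power unadjusted.
- **(b) Single-dose contrasts primary.** Restate the power as about 65% unadjusted, or about 53% with Bonferroni over two doses.

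In either case, state that d is assumed equal for both doses.

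**Cost.** Wording changes in the SAP (Estimation of sample size, demographic paragraph, AUC analysis) and in the protocol (Materials and Methods). The stated power becomes less favourable unless the pooled contrast is kept at near-equal totals. No extra participants are needed.
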